### 10.4 Scintigraphy

Patients will have the CNS (head and upper spinal cord) imaged by I-3F8 scintigraphy approximately 4, 24, 48 hours.

## 10.5 Concomitant Therapy:

Patients may receive systemic chemotherapy starting 3 weeks from the second injection of  $^{131}\text{I}$ -3F8. Patients must wait at least 3 weeks before they can resume injection 3 or 4. This will allow assessment of response while avoiding widespread progression of systemic disease.

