## **3.1 Background and Rationale**

### **3.2 Disease background**

With the central nervous system as a sanctuary site, it is increasingly recognized that improved treatment of systemic cancers is associated with a higher incidence of central nervous system relapse and neoplastic meningitis. By the time neuraxis metastases are clinically evident, limited palliative options exist; median survival time for most malignancies is 4-14 months. Stereotactic radiosurgery for small, single metastases (<4cm diameter), surgery for solitary metastases and radiotherapy are used for palliation. New techniques including preoperative functional imaging, image-guided neurosurgery, intraoperative ultrasound and cortical mapping have improved the success of aggressive surgical resection, and lowered the associated surgical morbidity and mortality. However, novel therapeutic agents that may prevent or delay the progression of disease are needed to improve overall outcome.

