## **4.1 Overview of Study/Design Intervention**

### **4.2 Design**

This is a phase II single-arm open-label study that will define responses to therapy with weekly intrathecal  $^{131}\text{I}$ -3F8 in patients with central nervous system/leptomeningeal GD2-expressing disease. Dosimetry at plaques of disease and surrounding normal tissues will be determined by a pre-treatment  $^{131}\text{I}$ -3F8 (2 mCi) scintigraphy. Pharmacokinetics of the dosimetry

dose of intrathecal  $^{131}\text{I}$ -3F8 will be determined by measurements of counts per minute (cpm) of serial CSF and serum samples.

Patients will then receive intrathecal  $^{131}\text{I}$ -3F8 treatment cycle (10 mCi/cycle) approximately weekly for a total of 4 cycles. A total dose of 40 mCi  $^{131}\text{I}$ -3F8 will be administered. Since the phase I study demonstrated a CSF dose of 15-60 cGy/mCi to the CSF, maximum total anticipated CSF dose of  $4 \times 10$  mCi of  $^{131}\text{I}$ -3F8 injections would be 600-2400 cGy; dose to the spinal cord and normal brain is negligible given the short range path length of  $^{131}\text{I}$ . At an estimated tumor to CSF dose ratio of 5:1, tumor dose could be as high as 3000-12000 cGy. Myelosuppression is not anticipated at this dose level. The chosen 40 mCi maximum  $^{131}\text{I}$  dose is considerably lower than the MTD reported using other intrathecal  $^{131}\text{I}$ -monoclonal antibodies for neoplastic meningitis on other phase I studies. To avoid the risk of radiation toxicity in patients who have had previous craniospinal radiation, the CSF radiation dose delivered by  $^{131}\text{I}$ -3F8 therapy injections will not exceed 2400 cGy based on the CSF dosimetry estimates from pre-treatment  $^{131}\text{I}$ -3F8 / scintigraphy scans. This may require the elimination and/or dose reduction of the 3rd or 4th injection for patients who have had previous craniospinal radiation. There will be no dose modifications for patients who have not had craniospinal radiation. Response to therapy will be assessed by neurologic examination, radiographic imaging and CSF cytology analysis. Other aims will be met by monitoring patients clinically and biochemically for toxicity and by serum assessment of HAMA.

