It is quite possible that  $^{131}\text{I}$ -3F8 may lead to disease stabilization without complete or partial responses in this population with advanced disease. We therefore propose overall survival at six months as the primary endpoint of this study. Leptomeningeal disease is rapidly fatal. Though some prior studies have reported survival at six months of around 15% these included patients receiving chemotherapy. Patients receiving  $^{131}\text{I}$ -3F8 at MSKCC have completed all chemotherapy and are not anticipated to have further oncologic treatment after progressing on this protocol. If  $^{131}\text{I}$ -3F8 has zero effect, we would therefore expect no more than 5% of patients to survive for six months. We will therefore use 5% overall survival at six months as the null hypothesis with 25% overall survival at six months as the alternative hypothesis.

Roadmap for the imaging dose of  $^{131}\text{I}$ -3F8

Day -5: Start SSKI and Liothyronine orally  
Day -1: Start Dexamethasone (start ~24 hrs pre-injection and tapered over ~1-2 days) orally  
Day 0: Injection of  $^{131}\text{I}$ -3F8 (2 mCi) intrathecally or by Ommaya

Roadmap for each weekly treatment cycle of  $^{131}\text{I}$ -3F8

Day -5: Start SSKI and Liothyronine orally  
Day -1: Start Dexamethasone (start ~24 hrs pre-injection and tapered over ~1-2 days) orally  
Day 0: Injection of  $^{131}\text{I}$ -3F8 (10mCi) intrathecally or by Ommaya

\* Dose adjustments for age <3 years based on CSF volume:

< 1 year: 50% dose reduction/injection

1-3 years: 33% dose reduction/injection

>3 years: Full dose 10 mCi  $^{131}\text{I}$ -3F8 per injection

\* Dose adjustments for patients with previous craniospinal radiation: The total maximum target CSF dose will be 2400 Gy. This may require a decrease or elimination of the 4th injection to prevent the risk of radiation toxicity for these patients. No dose adjustment will be made for patients who have not received prior craniospinal radiation.

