## **9.0 Treatment/Intervention Plan**

9.1 General outline: Following an initial test dose of 2 mCi  $^{131}\text{I}$ -3F8 for dosimetry, four weekly injections will be given via an Ommaya reservoir that will be placed by neurosurgery if not already present. If the patient has a ventriculoperitoneal shunt, and CSF flow study using the

shunt tubing has confirmed acceptable CSF flow, the shunt may be used for the administration of  $^{131}\text{I}$ -3F8. Patients can be treated in an outpatient setting or may be hospitalized overnight for supportive care after each injection. All patients will be monitored in accordance with Radiation Safety Guidelines. Patients are not anticipated to need isolation post-treatment.

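### Systemic chemotherapy is allowed from about day 28, but no MRI or CSF cytology is fixed before it, and section 14 does not separate responses or toxicities by chemotherapy

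*Combined protocol and SAP*

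**What the plan says.** Section 4.2 plans treatment "approximately weekly for a total of 4 cycles", and section 9.1 likewise says that "four weekly injections will be given via an Ommaya reservoir". Section 10.5 then provides: "Patients may receive systemic chemotherapy starting 3 weeks from the second injection of" 131I-3F8. It continues: "Patients must wait at least 3 weeks before they can resume injection 3 or 4". It gives the wait no starting event and no maximum, and does not call it an exception to weekly dosing. The stated purpose is: "This will allow assessment of response while avoiding widespread progression of systemic disease".

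On evaluation, section 4.2 names neurologic examination, imaging and CSF cytology as the response tools. Sections 4.2.2 and 10.1.3 place MRI at baseline and at an unspecified time after the last or 4th injection. The section 10 table lists MRI and cytology before the test dose and again 1-3 months after injection 4, with neither in between. Section 12.1 counts a patient as having an adequate trial after two injections and an extent-of-disease evaluation, which it does not date. Section 12.5.1 requires a CR to be confirmed at least 4 weeks later.

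On reporting, section 11.1 records toxicities until 30 days after the last dose. Section 14 promises counts of CR, PR, SD and PD, and toxicities by type and grade. It does not mention chemotherapy.

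**The concern.** Section 2.1 lists the response rate to 131I-3F8 and the cumulative toxicity of serial injections among its aims. Section 10.5 intends response to be assessed around the permitted chemotherapy, but nothing in the schedule secures an MRI or cytology before that chemotherapy starts. A response first seen afterwards enters the same count as one seen before.

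Toxicity is the clearer case. Section 4.2 states: "Myelosuppression is not anticipated at this dose level". If injection 3 or 4 is delayed, the blood count required before it (10.1.5) can follow chemotherapy and still fall inside the recording window. A chemotherapy cytopenia could then look like a new 131I-3F8 effect. Some attribution exists: 11.3 for grade 4 neurologic changes, 13.1 for grade 4 events leading to removal, and the relationship item in the SAE report (17.2). None of these separates chemotherapy in the section 14 tables or covers non-serious grade 1-3 events.

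Use of chemotherapy is foreseeable, because 6.1.4 admits patients with active cancer outside the CNS and 10.5 is written for them.

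**Working it through.** The plan gives no figure of its own to reproduce on this point, so the check is calendar arithmetic.

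**Inputs.** Weekly injections (4.2, 9.1) on days 0, 7, 14 and 21. Chemotherapy from 3 weeks after injection 2 (10.5). Follow-up 1-3 months after injection 4 (section 10 table), taken as 30-90 days. CR confirmation at least 28 days later (12.5.1). Toxicity recording to 30 days after the last dose (11.1).

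**Earliest chemotherapy.** 7 + 21 = day 28.

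**Response, weekly completers.**
- Tabulated MRI and cytology: 21 + 30 = day 51 to 21 + 90 = day 111. That is 51 − 28 = 23 to 111 − 28 = 83 days after the earliest chemotherapy.
- Time available to evaluate before it: 28 − 7 = 21 days after injection 2, or 28 − 21 = 7 days after injection 4. An MRI on days 21-28 would comply with 4.2.2 and 10.1.3, but nothing requires it.
- A first clear test on day 7 is confirmed no earlier than 7 + 28 = day 35, and one on day 28 no earlier than day 56. Either way, confirmation follows chemotherapy begun on day 28.

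**Response, patients who pause for chemotherapy.** An MRI after injection 4 necessarily follows the chemotherapy. If the wait runs from chemotherapy on day 28, injection 3 falls no earlier than 28 + 21 = day 49. The gap from injection 2 is then at least 49 − 7 = 42 days, against 7 on the weekly plan. Injection 4 follows no earlier than day 56, and tabulated follow-up no earlier than 56 + 30 = day 86.

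**Toxicity window open after chemotherapy on day 28** (last dose + 30 − 28):

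| Course | Last dose | Days open |
|---|---|---|
| Stops after two injections | day 7 | 7 + 30 − 28 = 9 |
| Four weekly injections | day 21 | 21 + 30 − 28 = 23 |
| One injection after the pause | day 49 or later | at least 49 + 30 − 28 = 51 |
| Injections 3 and 4 both after the pause | day 56 or later | at least 56 + 30 − 28 = 58 |

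The last two rows assume the wait starts with chemotherapy on day 28. Counted from injection 2 instead, the next injection could fall on day 28 itself. The figures would then be 28 + 30 − 28 = 30 and 35 + 30 − 28 = 37, and the gap from injection 2 at least 21 days. For weekly completers the window shrinks if chemotherapy starts later, and is nil from day 51.

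**Weight of one response.** 1/18 = 5.6 percentage points in an 18-patient subgroup and 1/36 = 2.8 in the 36 with minimal-disease medulloblastoma. In the 17-patient cohort it is 1/17 = 5.9, but section 14 says the overall analysis is complete. The 36 with medulloblastoma in CR have no disease in which to show a response.

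**The case against.** The strongest reply is that the effect is narrow. Response counts and toxicity tables are descriptive. The chemotherapy is aimed at systemic disease, and section 3.2 begins "With the central nervous system as a sanctuary site", so CNS response may be only partly confounded. Section 4.2 says patients "have completed all chemotherapy and are not anticipated to have further oncologic treatment" after progressing, which suggests low uptake. Of the 36 + 36 + 18 + 18 = 108 added places, 72 are for medulloblastoma, a CNS tumour. For a weekly completer, day 28 comes after all four injections, so chemotherapy then is ordinary later treatment. The wait also reads naturally as a washout after chemotherapy. All of this stands, and it limits the weight of the point. It does not supply a dated evaluation or a reporting rule.

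Four stronger readings are tempting, and the documents do not support them.
- A reader might infer that no response evaluation precedes chemotherapy. Neurologic examinations are dated before each injection. They can show progression but cannot establish a CR, so the gap concerns MRI and cytology.
- A reader might infer that section 14 directs pooling, or assigns every low count to 131I-3F8. It is silent on both.
- A reader might take 58 days as the minimum window for anyone who pauses. Section 10.5 speaks of injection 3 or 4, and with only one injection after the pause the figure is 51.
- A reader might infer that the primary result is compromised. Six-month survival is counted from the first injection whatever the imaging date, and the decision rule does not use CR, PR or SD. Whether permitted chemotherapy weakens the basis of the 5% null is a separate question, which cannot be sized without uptake.

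**Conclusion.** The point holds as a cheap improvement. Section 10.5 names assessment of response as a purpose, but the schedule fixes no MRI or cytology that would achieve it before chemotherapy, and section 14 has no rule for what follows. In patients who receive chemotherapy, the response rate and cumulative toxicity can be confounded. The response side may be only partly affected. The toxicity side is clearest when an injection is delayed, because a scheduled blood count then falls after chemotherapy.

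The overall size is unknown, because the documents do not give uptake. Per patient, the exposed toxicity window runs from 9 days to at least 58, depending on the course, and one response is worth 2.8 to 5.6 points in the affected subgroups. These figures assume strict weekly dosing, 30-day months and chemotherapy on the earliest permitted day; the 51- and 58-day figures also assume that the wait runs from that day. The six-month survival decision is not touched by this gap.

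**What to change.** - **Data.** Record the start and last-dose dates of systemic chemotherapy. These dates would also show how far the chemotherapy-free premise in 4.2 was met.
- **Section 14, response.** Report as the 131I-3F8 response rate only responses first documented before the first chemotherapy dose. List later ones separately, and show the rate with and without them on the same denominator. Flag CRs confirmed only after chemotherapy and also show the rate without them. Do not present these figures as strict bounds: the lower rate still includes CRs whose confirmation followed chemotherapy, so it can be too high.
- **Section 14, toxicity.** Tabulate by onset before or after the first chemotherapy dose. A split by patient group would put a low count on day 21 into the chemotherapy table even when chemotherapy began on day 28.
- **Section 12.1.** Where the extent-of-disease evaluation is done after two injections, do it before chemotherapy starts.
- **Section 10.5.** State that the 3-week wait runs from the last chemotherapy dose, in line with 6.2.5, and that it is an exception to weekly dosing.

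The cost is a wording amendment and two dates per patient given chemotherapy. Some patients may need one MRI and CSF cytology earlier than they otherwise would. The headline response rate may be lower, cells in the toxicity tables will be smaller, and the gap before injection 3 or 4 lengthens when chemotherapy runs over several doses. Sample size, primary endpoint and 131I-3F8 dose do not change.

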## 11.0 Toxicities/Side Effects

11.1 Toxicities will be assessed via the NCI toxicity criteria (CTC 3.0). All toxicities will be recorded in CRDB until 30 days after the last dose of  $^{131}\text{I}$ -3F8.

11.2 Toxicities associated with  $^{131}\text{I}$ -3F8 include fever, headache, nausea and vomiting, pain, allergic reaction, and/or drug extravasation. Hospitalizations for therapy administration, hyperglycemia or lymphopenia related to dexamethasone and self-limited fever, vomiting, or headache will not be considered serious adverse events (SAE) and will not be reported to the IRB or FDA though they will be captured in the institutional database. However, life-threatening infections or other life-threatening side effects will be considered SAE's and will be promptly reported to the Institutional Review Board of MSKCC and to the FDA.

11.3 Neurologic changes during the study period which meet the criteria for grade 4 neurotoxicity will be assessed by study physicians as being unrelated, possibly or probably caused by the injection. In the absence of clear evidence of tumor progression, it may be assumed that new signs and symptoms are treatment related.

11.4 Any deaths will be reviewed during the study by the Principal Investigators prior to subsequent entry of further patients.

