## **2.1 Objectives and Scientific Aims**

- To determine whether, in patients with GD2-expressing central nervous system/leptomeningeal neoplasms, the activity of intrathecal  $^{131}\text{I}$ -3F8 is sufficiently promising to warrant further study. Promising activity is defined as a 6 month overall survival rate of 25% or more.
- To determine the response rate to  $^{131}\text{I}$ -3F8 in this population.
- To determine the cumulative toxicities of serial injections of intrathecal  $^{131}\text{I}$ -3F8.
- To describe the effects of HAMA (human-anti-mouse antibody) on cerebrospinal fluid (CSF) and serum pharmacokinetics following multiple injections of  $^{131}\text{I}$ -3F8

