#### **14.0 Biostatistics**

This is a phase II study to assess the clinical efficacy of weekly intrathecal  $^{131}\text{I}$ -3F8 for a new cohort of 17 patients with GD2-expressing central nervous system and leptomeningeal neoplasms. A "response" is defined as a patient being alive six months after their first treatment. We will test hypothesis that the proportion of responses is 25% or more against a null hypothesis that proportion of responses is 5% or less, with a power of 80% and an alpha of 5%. Using a Simon two-stage optimal design, nine patients will initially be accrued. If at least one responds, then a further 8 patients will be entered on study. If the total number of responses is three or more, the agent will be declared active. Under this design, the probability of declaring the agent inactive at the end of the first stage (0 / 9 responses) is 0.63 if the true response rate is 0.05. This probability decreases to 0.08 if the true response rate is 0.25. The probability of declaring the agent active (3 or more responses / 17) is 0.05 and 0.8 if the true response rate is 0.05 or 0.25, respectively. It is expected that 4-6 patients/yr will be enrolled and that this study can be completed within 2-3 years.

	Reject null hypothesis if:	Reject alternative hypothesis if:
First stage	-	0 / 9 responses
Second stage	$\geq 3$ / 17 responses	$\leq 2$ / 17 responses

The number of CRs, PRs, SDs and PDs will be reported. Toxicities will be reported by type and grade.

Three additional subgroups will be added for patients with: Medulloblastoma in CR (36 evaluable patients), Medulloblastoma with stable, but minimal disease (36 evaluable patients), and Retinoblastoma or Melanoma (18 evaluable patients). For patients with neuroblastoma or other cancers in the CNS, 18 additional evaluable patients will be added. We have completed the statistics for this agent overall which have shown efficacy on this phase II study; increasing the number of slots will allow for in depth statistical analyses within these subgroups of patients.

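### Systemic chemotherapy is permitted inside the toxicity recording window, and the planned table by type and grade does not separate its toxicity from that of 131I-3F8

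*Combined protocol and SAP*

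**What the plan says.** The third objective in section 2.1 is "To determine the cumulative toxicities of serial injections of intrathecal" 131I-3F8. The plan for meeting it is spread over several sections.

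- **Recording (11.1):** "All toxicities will be recorded in CRDB until 30 days after the last dose of" 131I-3F8. No exception is made for events that begin after another anticancer treatment.
- **Analysis (14.0):** "Toxicities will be reported by type and grade". This is the whole toxicity analysis.
- **Schedule (9.1):** after a 2 mCi test dose, "four weekly injections will be given via an Ommaya reservoir".
- **Concomitant treatment (10.5):** "Patients may receive systemic chemotherapy starting 3 weeks from the second injection of" 131I-3F8, and then "Patients must wait at least 3 weeks before they can resume injection 3 or 4".
- **Attribution:** under 11.3, grade 4 neurologic changes "will be assessed by study physicians as being unrelated, possibly or probably caused by the injection". Section 13.1 uses attribution to decide on removal from study. The serious adverse event report in 17.2 has a field for relationship to treatment, and 17.2.1 defines such events as grade 4 and 5 toxicities with listed exclusions.
- **Expected exposure (4.2):** the paragraph that sets the null hypothesis states that patients given 131I-3F8 have finished all chemotherapy.

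**The concern.** The table in 14.0 is meant to describe what repeated intrathecal 131I-3F8 does to patients. If some of them start systemic chemotherapy while events are still being collected, the table describes the combination, and a reader cannot tell which rows belong to which treatment. The plan guards against this at entry, since 6.2.5 excludes systemic chemotherapy in the 3 weeks before the start. The analysis has no matching provision for chemotherapy given afterwards.

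Two consequences matter. Section 4.2 says "Myelosuppression is not anticipated at this dose level", so a cytopenia caused by chemotherapy would stand in the table as an unexpected effect of the study drug. And if chemotherapy comes between injections 2 and 3, events recorded around the later injections could look like the accumulation that the third objective is looking for.

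**Working it through.** The plan gives no figure for this overlap, so there is none to reproduce. The check is date arithmetic on its own intervals.

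**Inputs.** Injection 1 is day 0 and injections are weekly (9.1), so injections 2, 3 and 4 fall on days 7, 14 and 21. Chemotherapy is allowed from injection 2 plus 21 days (10.5). Recording ends 30 days after the last dose (11.1).

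**Earliest chemotherapy:** 7 + 21 = day 28.

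**Uninterrupted weekly course.** Overlap = (day of last injection + 30) − 28.

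| Last injection | Day | Recording ends | Largest overlap | Share of the 30 days |
|---|---|---|---|---|
| 2 | 7 | 37 | 9 days | 9/30 = 30% |
| 3 | 14 | 44 | 16 days | 16/30 = 53% |
| 4 | 21 | 51 | 23 days | 23/30 = 77% |

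For the full course this is 23/51 = 45% of the time from injection 1. Counting from the test dose would lower that share. On this schedule nothing before day 28 is affected: the interval between injections 3 and 4, and the 7 days after injection 4, are free of permitted chemotherapy.

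**Course interrupted for chemotherapy.** Assume chemotherapy on day 28, and that the 3-week wait runs from that day (10.5 does not say from which date it runs). Injection 3 is then earliest on 28 + 21 = day 49 and injection 4 on 49 + 7 = day 56.

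- If injection 3 is the last, recording ends on 49 + 30 = day 79, and 79 − 28 = 51 days follow the chemotherapy start.
- If injection 4 is the last, recording ends on 56 + 30 = day 86, and 86 − 28 = 58 days follow it (58/86 = 67%).

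Here every event after injections 3 and 4 comes after chemotherapy has begun.

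**Blood counts.** Section 10.1.5 schedules counts before each injection and about 1 to 3 months after the fourth. On the uninterrupted course the first late count falls at about day 51, the end of the window, so a cytopenia between days 28 and 51 would mostly be found by unscheduled tests. On the interrupted course the counts before injections 3 and 4 come after the chemotherapy start and fall well inside the window.

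**Does anything in the analysis separate the two sources?** No section flags, splits or censors events by chemotherapy exposure. Relationship is available for serious events and grade 4 neurologic changes, but 14.0 does not refer to it. Other events have no stated attribution, apart from removal decisions. Section 11.3 also lets new signs be presumed treatment-related when tumor progression is not clear, without naming chemotherapy as an alternative cause.

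**The case against.** Recording every event regardless of cause is a sound, conservative safety convention. Toxicity here is descriptive, and no efficacy decision in 14.0 depends on it. Relationship to treatment is already planned for most grade 4 and 5 events, so the most serious part of the profile can be attributed from data in hand. Section 4.2 says chemotherapy is complete, which suggests that few patients would receive it. All of this stands, and it limits the point to how events are tabulated and to lower-grade events without attribution.

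It does not remove the point. Section 10.5 gives express permission, the table does not use the attribution that exists, and the conflict between 4.2 and 10.5 leaves actual use unknown.

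A reader might go further and infer any of the following, which the documents do not support:

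- **That the table is inflated by a known amount.** The documents give neither the proportion treated with chemotherapy nor its event rates.
- **That later injections are generally the most contaminated.** On the weekly plan injections 3 and 4 precede day 28. The resemblance to cumulative toxicity arises only in interrupted courses, whose frequency is unknown.
- **That marrow effects of the two treatments cannot be told apart.** Section 4.2 expects no myelosuppression from 131I-3F8, so cytopenia after chemotherapy is among the easier events to attribute.
- **That the main table should stop at the first chemotherapy dose.** In an interrupted course this would take all toxicity of injections 3 and 4 out of it, including acute fever, headache and vomiting, and so weaken the objective it is meant to protect.

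**Conclusion.** The point holds in a limited form. Followed as written, the plan pools chemotherapy toxicity with that of 131I-3F8 for any patient who receives permitted chemotherapy before recording ends. The exposed period is at most 23 of the 30 days after the last injection on the full weekly course. It is 51 or 58 days of recording in the interrupted course worked above. The 23 days assume chemotherapy on the first permitted day. The 51 and 58 days also assume that the 3-week wait runs from that day and that injections resume at the earliest date.

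The number of patients affected, and so the size of any distortion, cannot be derived from the documents. A difference in distortion between disease cohorts is possible but is conjecture. The change is still worth making: it costs little if few patients receive chemotherapy, and it is needed to interpret the toxicity data if many do.

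**What to change.** - **11.1:** record the start date and agents of any non-protocol systemic chemotherapy given before recording ends.
- **14.0:** define the main table as all events from the first 131I-3F8 injection, expressly including the 2 mCi test dose, to 30 days after the last dose. Do not censor it at chemotherapy start.
- **14.0:** add the same table split by onset before versus on or after the first chemotherapy dose. Within the later part, identify whether the event followed injection 3 or 4.
- **4.2 and 10.5:** reconcile the statement that chemotherapy is complete with the permission to give it.

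The cost is a few sentences, one more table, and one date with the agents for each patient who receives chemotherapy. No event is lost and no treatment rule changes. The limitation is that events in the post-chemotherapy part remain of mixed cause; the split shows where that uncertainty lies but does not resolve it.
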